### 3. INTERIM ANALYSIS AND DATA REVIEW COMMITTEE

A Data Monitoring Committee (DMC) was planned to specifically review the safety data at three specific time points to ensure safety of the subjects:

- Review blinded safety data (2 weeks of follow up) after 30% of subjects have received their first injection to decide whether further dosing can continue;
- Review unblinded safety data (2 weeks of follow up) after 10% of subjects have received their third injection to decide whether further dosing can continue;
- Review unblinded safety data (2 weeks of follow up) after 30% of subjects have received their third injection to decide whether further dosing can continue.

These analyses are described in a separate document DMC Charter and DMC SAP.

### 4. SUBJECT INFORMATION

Subject information will be analyzed based on the FA analysis set unless otherwise specified.

Continuous variables will be summarized using the following statistics, as appropriate: number of observations, arithmetic mean (mean), 95% confidence interval (CI) for the mean, standard deviation (SD), standard error (SE), median, quartiles (Q1 and Q3), minimum and maximum. The minimum and maximum will be presented to the same number of decimal places as the original data. The mean and median will be rounded to one more decimal place than the original data, while the SD, SE and 95% CI to two more decimal places.

#### 4.1. Demographics and Baseline Characteristics

The following demographic and baseline characteristics will be summarized.

- Sexa (Female/Male)
- Age (years)
- Race
- Ethnicity
- Region
- Country
- Height (cm)
- Weight (kg)
- BMI (kg/m^2), calculated from the recording of baseline height and weight.

#### 4.2. Disposition Information

Number and percentage of subjects that were 1) screened, 2) screening failures, 3) subjects meeting eligibility criteria 4) randomized and vaccinated, 5) randomized not vaccinated and 6) vaccinated but not randomized will be tabulated.

Number and percentage of subjects that completed and those who discontinued together with the reason(s) for discontinuation will be tabulated. This will be done for completion/vaccine discontinuation from further vaccination and from the trial at Week 96 , at the end of LTE. Number and percentage of subjects at each planned LTE visit will also be tabulated.

#### 4.3. Concomitant Medications

The analysis of concomitant medications will be using the WHO drug dictionary as provided in the clinical database.

---

a At screening

Based on their start and stop date, concomitant therapies will be reported in each period during which they were applied.

If a concomitant therapy record misses components of its start and/or stop dates (Day and/or month and/or year):

- In case of partial start or stop dates, the concomitant therapy records will be allocated to periods using the available partial information, without imputations. If, for example, only month and year are available, these will be compared to the month and the year of the periods, and the concomitant therapy record will be allocated to the period(s) where these date parts match.
- In case of a completely missing start date, the concomitant therapy will be considered as having started before the trial.
- In case of a completely missing end date, the concomitant therapy will be considered as ongoing at the end of the trial/cut-off date.

Concomitant therapies will be tabulated. There will be special attention to Acetaminophen, NSAIDS or Antihistamines to identify medication that can mask local or systemic solicited events in the 8 days after the vaccinations and to Glucocorticosteroids for possible influence on immunogenicity results. Glucocorticosteroids will be flagged in the overall CM listing. After Week 96 only specific CM were to be collected (CTP Section 8) thus the reporting for the LTE will be limited to those as required by CTP.

#### 4.4. Exposure

Number and percentage of subjects by number of received vaccinations will be tabulated.

Tabulation of vaccine administered within and outside the protocol-specified time windows (-1/+3 weeks of the planned vaccination and additional 2 weeks) will be provided as well.

#### 4.5. Protocol Deviations

All major protocol deviations will be listed.

#### 4.6. Medical History

Medical history data will be listed.

### 5. SAFETY

The safety and tolerability endpoints are:

- Unsolicited AEs 28 days following each vaccination
- Solicited local and systemic AEs (reactogenicity), collected daily from day of vaccination for 7 days post-vaccination (day of vaccination and the subsequent 7 days).

The safety and tolerability analysis will be performed on the FA set. Specifically, the analysis for solicited adverse events will be done on those subjects in the FA set for whom reactogenicity assessments are available in the database (either via on-site assessments or via the diary pages of the CRF).

Safety data will be tabulated per period by regimen. Only the active periods will be shown in the tables (AE, Lab, VS and ECG), except for SAEs and HIV infections. In addition, for a selection of tables (AE, Lab), tabulations per subject by vaccine and per dose by vaccine will be provided. During the LTE only for SAEs and HIV infections will be collected.

In the 'per subject by vaccine' analysis, the safety will be presented per periods (post-dose 1, 2, 3, 4) by vaccine rather than by regimen. A 'post any dose' period (= regimen phase in section 2.1) will be added, that summarizes the safety after all administered doses of a vaccine. The post-any-dose period allows determining how many subjects reported events after administration of a certain vaccine regardless the number of doses. Each subject is counted only once. In case a subject has the same event after more than one dose, it is counted only once (and in case of showing attributes, the worst corresponding attribute is shown) in the post-any dose period. The denominator is the number of subjects that received the considered vaccine in the considered period.

In the 'per dose by vaccine' analysis, the safety will also be presented by vaccine. This table allows determining the incidence of events per administered dose of a certain vaccine. For example, if a subject has the same event at least

once after dose 1 and at least once after dose 2 of the same vaccine, it is counted 2 times (so the numerator is the sum of post-dose 1, 2, 3 and 4 events in the “per subject by vaccine” table). In case of showing attributes, the worst corresponding attribute of each period are shown. The denominator is the total number of doses administered of the considered vaccine over all subjects.

At the 3th and 4th vaccination timepoint two vaccines should be administered at two different injection sites (left/right deltoid). The local solicited events should be linked to the medication injected in that specific injection site. However for some subjects the link between local AE and injection site might be unavailable, so the AE will be attributed to both medications received by the subject (e.g. if a subject receiving Ad26 + gp140 HD with AE “Erythema”: Erythema will be counted for Ad26 and for gp140 HD). Systemic solicited and unsolicited AE will be reported under both the administered medications.

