9.3. Safety Evaluations

9.3.1. Endpoints

Safety and tolerability endpoints:

- AEs until Week 96 and local and systemic reactogenicity rates for 8 days after each vaccination.
- Discontinuations from vaccination/from study due to AEs.
- SAEs during the course of the study.

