9.3.2. Evaluations

Any clinically relevant safety-related changes that occur during the study must be recorded in the CRF.

Any clinically significant abnormalities persisting at the end of the study/early withdrawal will be followed by the investigator until resolution or until a clinically stable endpoint is reached.

The study will include the following evaluations of safety and tolerability according to the time points provided in the Time and Events Schedule:

Adverse Events

AEs will be recorded from signing of ICF until the final visit of the main study (Week 96). SAEs (including HIV infection and abnormal pregnancy outcome) will be recorded for the duration of the study, including the optional LTE phase (Group 1 and Group 2 only). AEs will be followed by the investigator as specified in Section 12.

Details regarding the PSRT and the DMC are provided in Sections 11.7 and 11.8, respectively.

Cardiac-Related Events

At study visits, subjects will be specifically questioned about cardiac-related events, including chest pain/pressure, shortness of breath, and peripheral edema. Any suspicion of a cardiac event will be evaluated clinically by history and physical examination, ECG (read by a central reading cardiologist), and quantitative troponin assay. In the event of an elevation of troponin and/or pathologic ECG changes, the subject will be sent for evaluation by a local cardiologist.

Solicited Adverse Events

Solicited AEs are precisely defined events that subjects are specifically asked about and which are noted by subjects through the memory aid. The investigator or his/her designee should discuss the information from the memory aids with subjects, document relevant information in the clinic chart (source document) and complete the relevant parts of the CRF as described in the CRF Completion Guidelines.

Injection Site (Local) Reactions

Subjects will be asked to note occurrences of erythema, induration and swelling (measured using the ruler supplied), and pain/tenderness, itching, or warmth at the injection site daily for 8 days post-vaccination (day of vaccination and the subsequent 7 days). These occurrences should be recorded through the memory aid provided to serve as a reminder to the subject for the next clinic visit.

Solicited Systemic AEs

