## NOTE:

a The start time of screening phase is 00:00. In case an earlier date is available (e.g. for lab or vital signs then use the very first date in order to include all data)

b In case a dose is not administered, the observations end up in the previous Follow-Up phase

c This timepoint is intended to be at the end of the main study i.e. Week 96, cut-off used is 29AUG2017. LTE data will be reported separately

For the immunogenicity analyses no phases will be constructed.

The periods/phases will be used primarily for safety and concomitant medication allocation. The post-dose periods (and the regimen phase) are considered active periods/phase, the screening and follow-up phases are considered non-active phases. There will be no phase defined for the LTE part of the study.

For descriptive statistics over time, assessments (regardless of the investigated parameter) will be allocated to an analysis visit based on the visit number as captured in the database.

For subjects that received a first dose, but did not receive a 2nd dose while still continuing their planned visit schedule, the measurements after the planned but not administered 2nd dose will not be included in graphs and tables showing descriptive statistics over time. Those measurements will be shown in listings but it will be indicated that these are not used in the analysis. Moreover, the vaccinations done after a missed one will be not be shifted to the previous one but will be considered as planned: in the example above if the 2nd is missed, the 3rd vaccination will still be reported as post-dose 3.

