### 5.1.1. Definitions

Emerging adverse events will be defined as any AE starting or worsening on or after the start of the first vaccination on Day 1.

Solicited AEs are precisely defined events (local and systemic) that subjects are specifically asked about and which are noted by subjects in the memory aid. Unsolicited AEs are all AEs that a subject experienced, but were not specifically asked about.

Both systemic solicited and unsolicited AEs will be considered to be related to the use of the study vaccine if the attribution is possibly, probably or very likely. An AE will be considered not related with the use of the study vaccine if the attribution is not related or doubtful.

Relationship of all AEs (systemic solicited and unsolicited) to the study vaccine will be assessed by the investigator. Local solicited AEs will always be considered as related to the injection.

The severity of the AEs will be classified as Mild, Moderate, Severe, Life-threatening or Fatal.

The grading of the adverse events will occur according to the DAIDS grading list (see CTP appendix 1).

Period allocation of AEs is defined in Section 5.1.3.

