### 5.1.2. Analysis of Adverse Events

AEs (unsolicited and solicited AEs) will be tabulated by presenting the number and percentage of subjects having at least one of the observed AEs.

The unsolicited AEs will be summarized by System Organ Class and Preferred Term. The solicited AEs will be summarized by class (local, systemic) and solicited term. For solicited as well as unsolicited AEs, tables focusing on severity, relatedness and both grade 3 severity and relatedness to vaccine will be created. SAEs, AEs with fatal outcome and AEs leading to permanent stop will also be tabulated. Separate summary tables for the solicited and the unsolicited events will be produced.

Events of interest (confirmed HIV infection) will be tabulated.

For the solicited local and systemic AEs, the duration and time to first onset of the events may also be summarized. If a subject experiences more than one occurrence of a solicited event, the maximum duration of the events will be used. The time to first onset is defined as (date of first onset – reference date + 1). The reference date is the date of the respective vaccination.

AEs summary tables for solicited and unsolicited AEs, tabulation of AEs by worst severity for the solicited AEs and overall incidence tabulation will be provided by subgroups (section 2.4) per period by regimen.

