#### STEP 2: combining events

Overlapping/consecutive events are defined as events in the same subject with the same preferred term which have at least 1 day in overlap or for which the start date of an event is 1 day after the end date of the preceding event. Overlapping/consecutive events may be combined into one AE or not, according to the following rules:

- 1) In case a non-active period (e.g. Screening) is followed by an active period, and the overlapping/consecutive events start in both periods, they are allocated to their respective period and are considered as separate events.
- 2) In case overlapping/consecutive events start within a single period, they are considered as one and the same AE. The individual events that contribute to this AE are retained as individual records in the ADAM database but are assigned the same onset, period, and total duration.
- 3) In case an active period is followed by a non-active period (e.g. Follow-Up), and the overlapping/consecutive events start in both periods, they are allocated to the active period and are considered as one and the same AE. The individual events that contribute to this AE are retained as individual records in the ADAM database but are assigned the same duration, onset and active period.
- 4) In case an active period is followed by an active period, and the overlapping/consecutive events start in both periods, they are allocated to their respective period and are considered as separate AEs. The same rule applies for 2 non-active periods.

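### SAP Section 5 leaves non-serious unsolicited AEs that start in follow-up without a planned table, although the protocol endpoint runs to Week 96

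*SAP*

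**What the plan says.** **Protocol.** Section 9.3.1 gives the first safety endpoint as "AEs until Week 96 and local and systemic reactogenicity rates for 8 days after each vaccination". Section 9.3.2 has all AEs collected from consent to the Week 96 visit; only the long-term extension is restricted to SAEs. Section 11.5 says the AE analysis includes events with onset in the treatment period, a term it does not define.

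**SAP.** Section 5 restates the unsolicited part of that endpoint as "Unsolicited AEs 28 days following each vaccination" and sets the display rule "Only the active periods will be shown in the tables (AE, Lab, VS and ECG), except for SAEs and HIV infections". Section 2.1 makes the four post-dose periods, which together form the regimen phase, the active ones, and says that "the screening and follow-up phases are considered non-active phases". Section 5.1.1 has no such limit: "Emerging adverse events will be defined as any AE starting or worsening on or after the start of the first vaccination on Day 1". Section 5.1.2 adds that "SAEs, AEs with fatal outcome and AEs leading to permanent stop will also be tabulated". Section 1 records that the Week 96 analysis has been done and will not be repeated.

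**The concern.** The SAP replaces a protocol endpoint with a shorter one and gives no reason. The display rule then removes the remaining events from the tables, although the SAP's own definition counts them as emerging.

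Safety and tolerability is a primary objective, and the trial is first-in-human for Ad26.Mos.HIV. If the SAP is followed exactly, the planned tables cannot show, by regimen, how many subjects had an unsolicited AE, or a related Grade 3 AE, up to Week 96. Cardiac symptoms, for example, are asked about at visits to Week 96, but a non-serious cardiac AE that first appears at Week 60 would be collected and not tabulated.

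**Working it through.** **Step 1. Does any SAP rule bring follow-up events back into a table?**

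Take a non-serious, related, Grade 3 unsolicited AE with onset at Week 60 (Day 421) in a subject who received all four doses.

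- *Allocation.* SAP 5.1.3, Step 1 allocates by start date. Post-Dose 4 ends at the later of 28 days and the 4-week visit, so the event falls in Follow-Up 4.
- *Emergence.* It started after the first vaccination, so it is emerging under SAP 5.1.1.
- *Display.* Follow-Up 4 is non-active, and the event is neither an SAE nor an HIV infection, so Section 5 keeps it out of the AE tables.
- *Post-any-dose period.* SAP 5 equates this with the regimen phase, which in Table 3 contains only Post-Dose 1 to 4. It does not reach the event.
- *Merging.* Under SAP 5.1.3, Step 2, when overlapping or consecutive events with the same preferred term start in an active and then a non-active period, "they are allocated to the active period and are considered as one and the same AE". This rescues continuations, not new events.
- *Discontinuation.* SAP 4.2 tabulates reasons for discontinuation. SAP 5.1.2 also plans a table of AEs leading to permanent stop, but does not say whether the active-period limit applies to it.
- *Listings.* SAP 5.1 names no AE listing.

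The event therefore has no planned table.

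**Step 2. How much of the main study is affected?**

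The documents state no figure to reproduce. Inputs are the nominal dose days 1, 85, 169 and 337 and the Week 96 visit on Day 673 (protocol schedule and Section 9.1.2), with 28 days per post-dose period (SAP Table 3).

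| Follow-up phase | Weeks | Length (weeks) | Days |
|---|---|---|---|
| 1 | 4–12 | 8 | 56 |
| 2 | 16–24 | 8 | 56 |
| 3 | 28–48 | 20 | 140 |
| 4 | 52–96 | 44 | 308 |
| Total | | 80 | 560 |

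- Total time: 673 − 1 = 672 days. Active: 4 × 28 = 112 days (16.7%). Outside: 560/672 = 83.3%.
- If every 4-week visit falls on its latest allowed day (+3), each active period lasts 31 days: 4 × 31 = 124, and 672 − 124 = 548; 548/672 = 81.5%.
- Counting calendar days inclusively, 31 days to 23:59 makes 32 dates: 4 × 32 = 128, and 673 − 128 = 545; 545/673 = 81.0%. On that convention the nominal case is 4 × 29 = 116, and 557/673 = 82.8%.
- Between doses: 8 + 8 + 20 = 36 weeks. After Week 52: 44 weeks. Before Week 28: 8 + 8 = 16 weeks, or 16/80 = 20%.

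The share is larger for subjects who stop vaccination, because a note to SAP Table 3 puts the time after an omitted dose in the previous follow-up phase. With three doses, active time is 3 × 28 = 84 days, and 588/672 = 87.5% lies outside.

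**Step 3. Safety laboratory visits (secondary).**

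The schedule has 15 post-baseline safety-laboratory visits: Weeks 2, 4, 12, 14, 16, 24, 26, 28, 36, 48, 50, 52, 60, 78 and 96. Eight lie in active periods (Weeks 2, 4, 14, 16, 26, 28, 50, 52). Seven do not: three pre-dose samples (Weeks 12, 24, 48) and four follow-up visits (Weeks 36, 60, 78, 96).

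**The case against.** The best defence is that 9.3.1 only marks where AE collection ends for the main study, and that Section 11.5, the analysis section, confines the AE analysis to a treatment period whose details the SAP may settle. A 4-week window also matches the one used for the study holding rules. This does not remove the gap. No protocol passage gives a 28-day limit for AE analysis. Even if the treatment period is read as the 48-week vaccination period, Follow-Up 1 to 3 lie inside it, and 56 + 56 + 140 = 252 of 336 days (75%) would still be untabulated.

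Second, Section 11.5 allows summaries, listings or narratives for severe AEs with no 28-day limit. That is true, but the provision is optional and SAP 5.1 does not take it up.

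Third, SAP 5.2 determines laboratory grades for each trial phase, and 5.2.1 lists Grade 3 and 4 toxicities. Section 5 still confines the laboratory tables to active periods, but the listing makes the laboratory point minor.

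What stands is that the percentages measure time, not events. No formal safety testing is planned, so no test result is at risk. The data exist, so the missing counts could be produced. The Week 96 outputs are not among the documents, so this point concerns what the SAP plans, not what was reported.

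**Conclusion.** The concern holds and should be fixed. The SAP's stated display rule drops part of a protocol safety endpoint: non-serious unsolicited AEs, other than HIV infection, that first start in Follow-Up 1 to 4. The affected time is 81.0% to 83.3% of the period from first dose to Week 96 for a subject who receives all four doses and completes the main study. The range depends on when the 4-week visits fall and how days are counted. It assumes doses and the Week 96 visit on their nominal days. The number of AEs affected is not in the documents.

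The gap is bounded. SAEs and HIV infections are tabulated throughout, continuations of post-dose events are merged back, and discontinuation reasons are tabulated. The effect on regimen selection at Week 28 is limited; the final safety report bears most of it.

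**What to change.** - Keep the 28-day tables; they are a reasonable display of events close to vaccination.
- Add, as supplementary output, by-regimen tables of unsolicited AEs with onset from Day 1 to Week 96: any, related, and Grade 3 or higher. The end-of-study analysis is a natural place for them.
- State in SAP 5.1.2 that the table of AEs leading to permanent stop is not limited to active periods.
- Align the endpoint wording in SAP 5 with protocol 9.3.1, and define the treatment period of protocol 11.5.
- As a secondary step, extend the worst-grade laboratory table to the follow-up phases.

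The cost is a few tables and some SAP wording. The data are collected, and SAP Table 3 already defines the phases. Wording changes alone would not be enough: with the Week 96 analysis finished and not to be rerun, they would change no output.

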## 5.1. Adverse Events

The analysis of AEs will be based on the MedDRA coded terms as provided in the clinical database.

### 5.1.1. Definitions

Emerging adverse events will be defined as any AE starting or worsening on or after the start of the first vaccination on Day 1.

Solicited AEs are precisely defined events (local and systemic) that subjects are specifically asked about and which are noted by subjects in the memory aid. Unsolicited AEs are all AEs that a subject experienced, but were not specifically asked about.

Both systemic solicited and unsolicited AEs will be considered to be related to the use of the study vaccine if the attribution is possibly, probably or very likely. An AE will be considered not related with the use of the study vaccine if the attribution is not related or doubtful.

Relationship of all AEs (systemic solicited and unsolicited) to the study vaccine will be assessed by the investigator. Local solicited AEs will always be considered as related to the injection.

The severity of the AEs will be classified as Mild, Moderate, Severe, Life-threatening or Fatal.

The grading of the adverse events will occur according to the DAIDS grading list (see CTP appendix 1).

Period allocation of AEs is defined in Section 5.1.3.

